3.15 Safety Analysis

Safety will be evaluated by scheduled monitoring of AEs, vital signs, clinical laboratory measurements, ECGs, and PEs. By-participant listings of all measurements and parameters will be presented in tabular format, including absolute values and changes from baseline (if applicable), by study period, dose cohort (as applicable), and study day.

Safety results will be presented separately for each of the 3 study Periods (DEP, RWP, and OLE). For the DEP, safety analyses will be performed on the DEP SAS. For the RWP and OLE study parts, safety analyses will be performed on the corresponding SAS, with results being presented for the responder and nonresponder populations as well as the overall population.

Additionally, adverse events will also be presented across the 3 Study Periods (i.e., DEP, RWP, and OLE) as discussed in [Section 3.15.1.7](#).

3.15.1 Adverse Events

Adverse events will be coded using the Medical Dictionary for Regulatory Activities (MedDRA) Version 25.1 (or higher) and will be classified using SOC and PT (with the exception of diarrhea and nausea AEs as discussed in Section 3.15.1.1). Severity of AEs and laboratory abnormalities will be graded using the National Cancer Institute Common Terminology Criteria for Adverse Events. Adverse events causality will be dichotomous: Related or Unrelated (i.e., as defined in Section 6.1.2 of the study protocol).

Treatment emergent adverse events (TEAEs) are any adverse events occurring or worsening in severity after the first administration of SYNB1934v1 study medication.

TEAEs will be tabulated by study Part, treatment group (for Part 2), system organ class, and preferred term. Incidence tables of participants with TEAEs will be presented for all TEAEs by maximum severity, serious AEs (SAEs), TEAEs assessed as related to IMP, and TEAEs resulting in discontinuation of study dosing.

The number and percentage of participants who experienced at least one TEAE as well as the number and percentage of participants who experienced each specific SOC and PT will be presented. For the

presentation of TEAE incidences, the SOCs will be sorted alphabetically, and within SOC, the preferred term (PT) will be used and presented by decreasing total frequency.

3.15.1.1 Adverse Events Severity

The severity rating of an AE refers to its intensity. The severity of each AE will be categorized using the NCI CTCAE. For any term that is not specifically listed in the CTCAE scale, intensity should be assigned a grade of 1 through 5 using the following CTCAE guidelines:

- Grade 1: Mild; asymptomatic or mild symptoms; clinical or diagnostic observations only; intervention not indicated.
- Grade 2: Moderate; minimal, local or noninvasive intervention indicated; limiting age-appropriate instrumental activities of daily living.
- Grade 3: Severe or medically significant but not immediately life-threatening; hospitalization or prolongation of hospitalization indicated; disabling; limiting self-care activities of daily living.
- Grade 4: Life-threatening consequences; urgent intervention indicated.
- Grade 5: Death related to AE.

Exceptions to CTCAE criteria will be implemented for grading certain gastrointestinal-related TEAEs, as detailed in Table 9.

Table 9: Severity Assessment of Diarrhea and Nausea

Grade	Diarrhea ^a	Nausea
1	Increase of diarrhea, < 3 liquid stools a day over baseline; mild increase in ostomy output compared to baseline	Loss of appetite without alteration in eating habits and/or with use of planned anti-nausea medication
2	Diarrhea ≥ 3 liquid stools daily and limiting instrumental ADLs	Use of unplanned concomitant medications to increase oral intake
3	Diarrhea requiring hospitalization or limiting self-care ADLs	Inadequate oral caloric or fluid intake; tube feeding, TPN or hospitalization indicated (unchanged from CTCAE)
4	Life-threatening consequences; urgent intervention indicated (unchanged from CTCAE)	Not applicable
5	Death (unchanged from CTCAE)	Not applicable

ADLs = activities of daily living; CTCAE = Common Terminology Criteria for Adverse Events, TPN= Total parenteral nutrition.

^a Diarrhea is defined as liquid stools without consistency in shape.

3.15.1.2 Adverse Events Causality

An adverse event will be assessed a causality of Related/Not Related to each the following:

- SYNB1934v1
- PPI.

3.15.1.3 Adverse Events of Special Interest

As discussed in Section 6.3 of the study protocol, adverse events of special interest (AESIs) for SYNB1934v1 are as follows:

- Hypersensitivity reactions due to SYNB1934v1
- Infections due to SYNB1934v1
- Grade ≥ 3 gastrointestinal AEs per protocol specified grading criteria, including nausea, vomiting, diarrhea, and abdominal pain.

3.15.1.4 Adverse Event Missing Date Imputation

The following rules apply when determining if an AE is treatment-emergent in the scenario where the start date is missing or partially missing. These rules provide an algorithm to “impute” a complete AE start date which will then be used to determine if the AE is treatment emergent.

AE Start Date Imputation

AE start date missing day and month:

- If the year is the same as the year of the treatment start date, the day and month of the date of treatment start date will be assigned to the missing fields
- If the year is prior to the year of the treatment start date, December 31 will be assigned to the missing fields
- If the year is after the date of the treatment start date, January 1 will be assigned to the missing fields.

AE start date missing month only:

- The day will be treated as missing, and both month and day will be replaced according to the above procedure.

AE start date missing day only:

- If the month and year are the same as the month and year of the treatment start date, the day of the treatment start date will be assigned to the missing day
- If either the year is before the year of the date of the treatment start date or if both years are the same, but the month is before the month of the treatment start date, the last day of the month will be assigned to the missing day

- If either the year is after the year of the treatment start date or if both years are the same, but the month is after the month of the treatment start date, the first day of the month will be assigned to the missing day.

AE start date completely missing:

- If the AE end date is complete and after the treatment start date, the treatment start date will be assigned to the missing start date
- If the end date is complete and before the treatment start date, the end date will be assigned to the missing start date
- Otherwise, the AE start date will be assigned the treatment start date.

If the end date is complete and the imputed start date as above is after the end date, the start date will be imputed by the end date.

AE End Date Imputation

The following is the algorithm to impute a missing AE end date.

AE end date year is missing or AE is “ongoing”:

- If the AE end date year is missing or is indicated as “ongoing” the AE end date will not be imputed.

AE end date missing day and month:

- If the AE end date day and month is missing the month and day should be set to the earliest of the following: 31DECYYYY, date of death, participant’s last visit date.

AE end date missing month only:

- The day will be treated as missing, and both month and day will be replaced according to the above procedure.

AE end date missing day only:

- If the AE end date day is missing the day should be set to the earliest of the following: last day of the month, date of death, participant’s last visit date.

3.15.1.5 Adverse Event Summaries

The following are the set of adverse event summaries.

- Overall summary of TEAEs
- Incidence of TEAEs by SOC and PT
- Incidence of TEAEs by SOC, PT, and Severity
- Incidence of TEAEs by SOC, PT, and Related to SYNB1934v1

- E.** Incidence of TEAEs by SOC, PT, and Related to PPI
- F.** Incidence of TEAEs Leading to Drug Interruption by SOC and PT
- G.** Incidence of TEAEs Leading to Dose Reduction by SOC and PT
- H.** Incidence of TEAEs Leading to Drug Discontinuation by SOC and PT
- I.** Incidence of AESIs by SOC, PT, and Severity
- J.** Incidence of Serious Adverse Events by SOC and PT
- K.** Incidence of SYNB1934v1 Related Serious Adverse Events by SOC and PT
- L.** Incidence of PPI Related Serious Adverse Events by SOC and PT.

For the DEP only:

- M.** Incidence of Adverse Events prior to first dose of SYNB1934v1 by SOC and PT by Dose Level
- N.** Incidence of Adverse Events prior to first dose of SYNB1934v1 which are PPI related by SOC and PT by Dose Level
- O.** Incidence of TEAEs by SOC and PT by Dose Level
- P.** Incidence of TEAEs by SOC, PT, and Severity by Dose Ramp Period
- Q.** Incidence of TEAEs by SOC, PT, and Related to SYNB1934 by Dose Ramp Period.

This set of analyses will be performed for each of the 3 study periods (DEP, RWP, OLE) separately using the corresponding SAS. The following conventions will be applied:

- For the DEP, the AEs summaries will be presented by SYNB1934v1 dose group and overall. The SYNB1934v1 dose group will be determined by the dose the participant was on at the TEAE start date
- For the RWP, the AEs summaries will be presented by SYNB1934v1 (i.e., each individual iTD dose and overall) and placebo and within these 2 treatment groups by: responder, nonresponder, and overall
- For the OLE, the AE summaries will be presented by responder, nonresponder, and overall. The SYNB1934v1 dose group will be determined by the dose the participant was on at the TEAE start date.

For the presentation of TEAE incidences, the SOCs will be sorted alphabetically, and within SOC, the PT will be used and presented by decreasing total frequency based on the total population.

For the overall summary of TEAEs (i.e., item **A** above), the following information will be provided:

- Number and percent of participants with a TEAE
- Number and percent of participants with a TEAE of Grade 1

- Number and percent of participants with a TEAE of Grade 2
- Number and percent of participants with a TEAE of Grade 3
- Number and percent of participants with a TEAE of Grade 4
- Number and percent of participants with a SYNB1934v1 related TEAE
- Number and percent of participants with a PPI related TEAE
- Number and percent of participants with an AE leading to treatment interruption
- Number and percent of participants with an AE leading to treatment discontinuation
- Number and percent of participants with an AE leading to dose reduction
- Number and percent of participants with an SAE
- Number and percent of participants with a SYNB1934v1-related SAE
- Number and percent of participants who died.

Additionally, for the adolescent subgroup, TEAEs will be summarized by PT and SOC for each of the 3 study periods (DEP, RWP, and OLE).

- For the DEP, the TEAEs summaries will be presented by SYNB1934v1 dose group and overall. The SYNB1934v1 dose group will be determined by the dose the participant was on at the TEAE start date.
- For the RWP, the TEAEs summaries will be presented by SYNB1934v1 (i.e., each individual iTD dose and overall) and placebo and within these 2 treatment groups.
- For the OLE the TEAEs summaries will be presented by SYNB1934v1 dose group and overall. The SYNB1934v1 dose group will be determined by the dose the participant was on at the TEAE start date.

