#### **4.3. Treatment of Participants**

Within this protocol, IMP refers to SYNB1934v1 or placebo.

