##### **4.3.4.1. Proton Pump Inhibitor**

During participation in the study, participants will take a PPI [REDACTED] [REDACTED] QD (recommended to occur before breakfast) starting 7 days before first dose of IMP in Part 1. The PPI should be taken at the same time each day, even if no meal is consumed. If participants are already on a PPI regimen consistent with instructions in the package insert, they

may continue on that and not [REDACTED]. If participants cannot tolerate a PPI, they can use an H2 blocker per investigator discretion. If neither a PPI nor H2 blocker are tolerated during the screening, the participant will discontinue the study. The dose of PPI or H2 blocker should remain stable for Parts 1 and 2 of the study; if a dose adjustment to the PPI or H2 blocker is required in Part 3, the investigator must discuss with the medical monitor (unless the adjustment is required due to an adverse event). If a PPI or H2 dose is missed, it should be taken as soon as realized and then resume the normal before-breakfast QD or BID schedule, according to the locally approved PPI or H2 label.

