c Participants who discontinue prematurely during the DEP will complete an early termination visit 30 days after the last dose of IMP as described in Table 6. Participants who discontinue prematurely during RWP will complete RWP study measures as scheduled prior to the early termination visit. Early termination visits are described in Section 5.6.

- d Participants may titrate down to the previous dose level during the iTD period if there is difficulty tolerating a higher dose level or at the investigator's discretion. Visits and blood draws occur after a participant has been at a dose level for 3 weeks (including the ramp of that dose level as shown in [Table 4](#)). Participants must remain on their iTD for 3 weeks before proceeding to Part 2. Participants cannot up-titrate again until the OLE.
- e Height and weight measured only at screening.
- f Serum pregnancy test at screening; urine pregnancy test at other visits.
- g All blood Phe should be drawn in duplicate. Baseline samples in DEP and RWP must be taken prior to the first doses in those periods. In Part 1, blood Phe will be measured every 3 weeks after a change in dose level during the iTD-finding period. In Part 2, blood Phe will be measured at Weeks 1, 3, and 4. See [Section 5.4.1](#) of the protocol for more information. Patients enrolled in the optional DEP weekly substudy will have weekly [REDACTED] See [Section 5.4.2](#) of the protocol for more information.
- h A 3-day dietary intake assessment will occur for 3 consecutive days prior to scheduled study visits and blood Phe draws. See Diet Manual for more information.
- i The first dose of a PPI will be taken on or before Day -7 and continue daily as described in [Section 4.3.4.1](#).
- j Investigational medicinal product should be taken within 30 minutes of finishing a meal. See the Diet Manual for further details.
- k Samples will be used for monitoring anti-drug antibodies as needed (see [Section 6.3](#)).
- l Fecal samples can be done at any time during the screening period, no less than 5 days prior to baseline visit.

**Table 6: Schedule of Events: Part 3, Open-Label Extension Period and Follow-up, End of Study and Early Termination Visits**

	Quarterly Visits	End of Study	Early Term.
	Every 90 days ± 5 days	at least 30 days after last dose	at least 30 days after last dose
Assessmenta (Protocol Section)			
Vital signs (SBP/DBP, pulse, body temperature) (5.5.2)	•	•	

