3.5 Analysis Populations

Analysis populations will be defined for each of the 3 parts of the study (DEP, RWP, and OLE).

Full analysis set (FAS): The full analysis sets are based on the intention-to-treat principle. The DEP FAS includes all participants enrolled in the DEP who take at least one dose of DEP study medication.

The RWP FAS is defined as all participants randomized into the RWP who take at least one dose of RWP study medication. Additionally:

- The responder RWP FAS is defined as participants in the RWP FAS who are responders
- The nonresponder RWP FAS is defined as participants in the RWP FAS who are nonresponders.

A responder is defined as a participant who achieves a $\geq 20\%$ reduction in blood Phe level compared to DEP baseline on SYNB1934v1.

The responder RWP FAS will be the primary efficacy analysis population for the RWP. Analyses on the RWP FAS will be performed according to the randomized treatment group.

In the event that, based on the interim analysis results utilizing the criteria provided in [Table 10](#), the DMC recommends dropping either the 1×10^{12} or the 1×10^{12} and 6×10^{11} doses the following will occur:

- The participants in the DEP who have an iTD corresponding to a dropped dose will go directly into the OLE part of the study (i.e., as opposed to being randomized into the RWP).
- The RWP FAS, responder RWP FAS, and nonresponder RWP FAS, will exclude all participants whose iTD dose level was dropped.

These participants who are excluded from the RWP FAS will be summarized separately.

Safety analysis set (SAS): For each of the 3 study parts, the SAS will include all participants who received any amount of IMP in the corresponding study part with treatment assignment based on the treatment received.

For the RWP the safety analyses will be presented for the RWP SAS overall as well as by responder/nonresponder subgroups. Similarly, the OLE safety analyses will be presented for the OLE SAS overall as well as by responder/nonresponder subgroups.

A participant will be considered receiving treatment if the eCRF question “did the patient receive any study drug doses” is answered “Yes” and there is a corresponding non-missing date.

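### Pre-dose adverse event tables (SAP 3.15.1.5, items M and N) leave out anyone who started the PPI but never received IMP, and their dose-level columns cannot be filled

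*SAP*

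**What the plan says.** Among the summaries for the DEP only, SAP 3.15.1.5 lists item M, "Incidence of Adverse Events prior to first dose of SYNB1934v1 by SOC and PT by Dose Level", and item N, "Incidence of Adverse Events prior to first dose of SYNB1934v1 which are PPI related by SOC and PT by Dose Level". The population is set just below the list: "This set of analyses will be performed for each of the 3 study periods (DEP, RWP, OLE) separately using the corresponding SAS". SAP 3.5 defines that set: "the SAS will include all participants who received any amount of IMP in the corresponding study part". Protocol 4.3 settles what IMP covers: "Within this protocol, IMP refers to SYNB1934v1 or placebo". The PPI is therefore not IMP.

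The PPI is compulsory and comes first. Protocol 4.3.4.1 has it "starting 7 days before first dose of IMP in Part 1", and a footnote to Protocol Table 5 says "The first dose of a PPI will be taken on or before Day -7". The same protocol section describes an exit before dosing: "If neither a PPI nor H2 blocker are tolerated during the screening, the participant will discontinue the study".

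For the columns, SAP 3.15.1.5 presents DEP events by dose group and overall, and assigns dose group by the dose being taken when the treatment-emergent event began.

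**The concern.** SAP 3.15.1.2 has every event judged for its relation to the PPI separately from SYNB1934v1, and item N is the only planned table of PPI-related harm before dosing. As specified, it covers only people who came through the run-in and were then dosed. Those who stopped because they could not tolerate acid suppression are the most informative cases for such a table, and they cannot enter it. The dose split adds a second fault, because events that precede any dose are to be laid out by dose.

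**Working it through.** The documents state no figure for this point, so there is nothing to reproduce. The check is a trace through the definitions, followed by an illustration on assumed counts.

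**Population**

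1. Items M and N use the DEP safety set (SAP 3.15.1.5). Protocol 8.10 also places DEP safety analyses on that set.
2. Membership requires some IMP in that part (SAP 3.5), and IMP means SYNB1934v1 or placebo (Protocol 4.3).
3. The PPI begins at least 7 days before IMP (Protocol 4.3.4.1 and Table 5), so there is a window with PPI exposure and no IMP.
4. Anyone who leaves in that window is outside the set, and so outside both numerator and denominator.
5. The events themselves exist in the data, since adverse events are recorded from signature of consent (SAP 2.4.1).

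No other planned summary table fills the gap:

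- Items E and L of SAP 3.15.1.5 (PPI-related TEAEs and PPI-related serious events) use the same set.
- The disposition summary in SAP 3.6.1 gives reasons for non-completion only for the three study parts. Its DEP percentages use the DEP FAS, which under SAP 3.5 also requires a dose.
- The screening-period diary summary in SAP 3.15.1.8 covers only bother scores for gastrointestinal events. It also refers to treatment-emergent events in screening, which the definition in SAP 3.15.1 does not allow.

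Item M is wider than the PPI run-in. It covers everything before the first dose, screening may last 45 days, and the PPI need only start by Day -7. A person who leaves between consent and the first PPI dose is therefore missing from M as well.

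**Columns**

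SAP 3.15.1 defines a treatment-emergent event as one that starts or worsens after the first SYNB1934v1 administration. An event in M or N has no dose at onset, so the dose-at-onset rule cannot place it in the 3 × 10^11, 6 × 10^11 or 1 × 10^12 column. The SAP gives no other rule. Using the first dose received would put everyone in one column, because all participants start at Dose 1. Only the overall column has a meaning, and only for people who were later dosed.

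**Illustration (all counts assumed)**

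Suppose 65 participants start the PPI, 6 of them have a PPI-related event before IMP, and 5 leave before IMP. Let k be the number of leavers with such an event.

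- Incidence in all starters: 6/65 = 9.2%
- Table N as specified: (6 − k)/(65 − 5) = (6 − k)/60

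| k | Table N | Against 9.2% |
|---|---|---|
| 0 | 6/60 = 10.0% | higher |
| 1 | 5/60 = 8.3% | lower |
| 2 | 4/60 = 6.7% | lower |
| 3 | 3/60 = 5.0% | lower |
| 4 | 2/60 = 3.3% | lower |
| 5 | 1/60 = 1.7% | lower |

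Table N understates the incidence when the event rate among leavers (k/5) exceeds the rate among all starters (6/65), and overstates it when the leavers' rate is lower.

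**The case against.** The strongest case on the other side is that little depends on these two tables. They are descriptive, and no endpoint, test or stopping rule uses them. PPI-related harm after dosing is reported in items E and L. People who leave before IMP leave during screening, and leaving them out follows the protocol's own rule for DEP safety. Few may leave this way: Protocol 4.2.2 excludes known intolerance to PPIs and H2 blockers, an H2 blocker is the fallback, and someone already on a suitable PPI may continue it. All of this stands, and it limits the weight of the point. It does not make table N a description of run-in tolerability.

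A reader might infer three stronger things that the documents do not support.

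- **That the PPI-related rate is certainly biased downward.** Leavers drop out of the denominator too, and people may leave before IMP for reasons unrelated to the PPI. In the illustration, k = 0 gives an upward shift.
- **That the dose split would make run-in events look dose-related.** That would need a rule sorting events by a dose reached later. The SAP contains none; under its actual rule the dose columns are empty.
- **That the events disappear from the report.** SAP 3.1.2 and 3.15 provide for data listings and by-participant safety listings, so the events may still be shown there. What is missing is their place in the incidence tables.

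**Conclusion.** The point holds as a minor safety-reporting correction. Two things follow from the definitions alone: a PPI-related event that leads to withdrawal before IMP is never counted in table N, and the dose columns of M and N cannot be filled. Understatement of the PPI-related incidence is likely, because people who leave through intolerance are those most likely to have had such an event, but it is not assured. Its size cannot be established, since the documents give no number or rate of run-in exits; the range of 10.0% to 1.7% against 9.2% rests wholly on the assumed counts. No efficacy conclusion is affected.

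**What to change.** In SAP 3.15.1.5:

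- Remove the split by dose level from items M and N and present each in one overall column.
- Base item N on all participants who took at least one dose of study PPI, or of the H2 blocker substituted for it, whether or not they later received IMP.
- Base item M on all consented participants, since it covers events from consent onward.
- Add to item N a row for discontinuation before the first dose due to a PPI-related event. Do not extend this row to H2-blocker-related events: causality is collected only against SYNB1934v1 or IMP and the PPI (SAP 3.15.1.2, Protocol 6.1.2), so an H2-blocker row would need new data collection.

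The cost is SAP wording, one population flag for item N, and carrying some screen failures into two descriptive tables. SAP 3.10.1 says PPI and H2-blocker use has its own eCRF page, but not that the page is completed for people who never reach IMP. That must be confirmed before the flag can be derived.
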